### Study information

Title	Non-interventional study describing direct costs related to anticoagulation treatment in patients with nonvalvular atrial fibrillation (NVAF) in secondary stroke prevention prescribed apixaban or warfarin treatment
Protocol number	B0661121
Protocol version identifier	1.2
Date	5. November 2018
Active substance	B01AF02 apixaban
Medicinal product	Eliquis
Research question and objectives	To describe the direct costs related to warfarin/apixaban treatment during the first 6 months of the secondary stroke prevention in NVAF patients.
Author	PPD MUDr. PPD Ph.D.

## 1. LIST OF ABBREVIATIONS

Abbreviation	Definition
AE	adverse events
AEM	adverse event monitoring
AF	atrial fibrillation
BMI	body-mass index
e-CRF	electronic case report form
EDP	exposure during pregnancy
FXa	coagulation factor Xa
IEC	Independent Ethics Committee
INR	international normalized ratios
IRB	Institutional Review Board
LSLV	last subject last visit
NIS	non-interventional study
NOAC	non-vitamin K antagonist oral anticoagulant
NVAF	non-valvular atrial fibrillation
SAE	serious adverse events
TIA	transient ischemic attack
VKA	vitamin K antagonists

## 3. ABSTRACT

None.

## 4. AMENDMENTS AND UPDATES

None.

## 5. MILESTONES

Milestone	Planned date
Completion of feasibility assessment	September 2018
Start of data collection	July 2020
End of data collection	September 2020
Final study report	November 2020

## 6. RATIONALE AND BACKGROUND

Patients with atrial fibrillation (AF) are at increased risk for stroke. AF is associated with a four to fivefold increase in risk of stroke and thromboembolic events, resulting in significant morbidity, mortality, and costs. Stroke is the second most common cause of death and major cause of disability worldwide. About 30% of strokes occur in individuals with a previous transient ischemic attack (TIA) or stroke, and more than 50% occur in individuals with previous vascular events of any kind.

Warfarin is a highly effective treatment, reducing the risk of stroke by about two thirds, but its effectiveness in clinical practice is challenged by its variable dose response, drug-food and drug-drug interactions, need for frequent monitoring of international normalized ratios (INR), and associated risk of hemorrhage. Bleeding complications are relatively frequent, and a high proportion of patients discontinues or receives suboptimal therapy in clinical practice. In recent, carefully monitored trials, patients treated with warfarin spent only 63–68% of the time in the therapeutic INR range. Warfarin is associated with bleeding and drug related hospitalizations relate to a narrow therapeutic window and difficulties in adjusting the dose. Among elderly patients (65 years and older) warfarin was the most common drug leading to drug related hospitalizations followed by insulins, oral antiplatelet agents, and oral hypoglycemic agents.

Bleeding among patients on anticoagulant therapy often leads to cessation of anticoagulant treatment, which may increase the risk of subsequent thrombotic events. Termination of warfarin after a gastrointestinal bleed was shown in one study to increase the risk of death and thrombotic events. In a real-world registry, patients who experienced serious bleeding had a threefold increase in the risk of thrombotic events even though the majority of patients did not permanently stop oral anticoagulation.

Non-vitamin K antagonist oral anticoagulants (NOACs) that have emerged in recent years as alternatives to warfarin are proven to reduce these events, similar to or more than warfarin, with a similar or lower risk of hemorrhage. Additionally NOACs have predictable effect without need for routine monitoring, and fewer food and drug interactions compared with vitamin K antagonists (VKA). Apixaban is a direct oral factor Xa inhibitor with rapid absorption, a 12-hour half-life, and 27% renal excretion. In patients with AF and at least one additional risk factor for stroke, the use of apixaban, as compared with warfarin, significantly reduced the risk of stroke or systemic embolism by 21%, major bleeding by 31%, and death by 11%. In the patients with AF who were not candidates for VKA treatment, apixaban was compared to aspirin (ASA) and showed significant reduction in rate of stroke and systemic embolism by 55% without increasing the risk of major bleeding.

Real-world clinical observations are justifying that improved clinical profile of NOACs is translated to hard end-points in clinical practice. Favorable effectiveness and safety together with easiness of monitoring and improved adherence are generating important savings in cost of healthcare services. According to *Laliberté et al.* the NOACs' (rivaroxaban) users have

significantly less AF-related hospitalization days than those patients who use warfarin. Apixaban was found to be a cost-effective alternative to warfarin for stroke prevention in patients with AF in Sweden, Portugal as well as in the USA and also (compared to warfarin) apixaban is a cost-saving medicine with significantly lower rates of stroke and major bleeding in a real-world nonvalvular atrial fibrillation (NVAF) population in the USA. In the group of NOACs apixaban seems to be the most cost-effective alternative in comparison to rivaroxaban and dabigatran.

NOACs are indicated for prevention of stroke and systemic embolism in patients with nonvalvular atrial fibrillation . When oral anticoagulation is initiated in a patient with AF who is eligible for a NOAC (apixaban, dabigatran, edoxaban, or rivaroxaban), a NOAC is recommended in preference to a VKA as stated in guidelines of European Society of Cardiology (endorsed by Czech Society of Cardiology) .

Nonetheless NOACs were categorized as a second line treatment due to the restriction of SUKL (local regulatory authority) in Czech Republic and therefore Czech patients are primarily treated with warfarin (including patient post stroke/TIA) and NOACs treatment can be initiated only in case of defined contraindication. Czech Cardiology Society, Society of Ambulatory Specialist together with main Czech Public Insurance House (VZP) defined number of conditions where safe and efficacious anticoagulation therapy by VKA cannot be adequately ensured. Prescription of NOACs as first line therapy is allowed in these defined situations . One of the situations is described as higher sensitivity to warfarin. There are two variants of two genes, CYP2C9 and VKORC1, account for 30-50% of the variability in dosing of warfarin. The prevalence of CYP2C9 (allele \*1, \*2 and \*3) and VKORC1 (-1639 G and A alleles), and their combinations in Czech population was analyzed and about 30% of the Czech healthy subjects have genetically determined higher sensitivity to warfarin. Individuals with higher sensitivity to warfarin are eligible for first line NOACs treatment in secondary prevention of stroke.

Additionally there is no healthcare resource use (hospitalization days, outpatient visits, and clinical events) comparison of apixaban to warfarin available in the Czech Republic. The most intensive resource use is expected in the first 6 months after stroke, especially because of a high risk of the event recurrence. Considering that there are less outpatient visits, less monitoring needed and lower risk of the complications and adverse events expected with apixaban. Real-world data about the impact of different treatment strategies on healthcare resource use and costs are essential arguments for establishing the clinical value of new therapies.

In the light of this situation we have designed this study to compare the healthcare resource use in patients who use warfarin or apixaban in secondary stroke prevention as a first line therapy.

## 7. RESEARCH QUESTION AND OBJECTIVES

The primary objective of the study is:

- Description of direct costs related to warfarin/apixaban treatment during the first 6 months of the secondary stroke prevention in NVAF patients.

The secondary objectives of this study are:

- Comparison of direct costs related to warfarin/apixaban treatment during the first 6 months of the secondary stroke prevention in NVAF patients;
- Number of hospitalization days in the first 6 months of the treatment;
- Number of ischemic/hemorrhagic strokes in the first 6 months of the treatment;
- Number of ischemic events in the first 6 months of the treatment;
- Number of major/minor hemorrhagic events in the first 6 months of the treatment;
- Mortality rates in both cohorts;
- Number and costs of medical procedures directly related to the treatment in the first 6 months (visits, hospitalizations, labs, diagnostics, etc.);
- Overall safety (adverse events) of the treatment.

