## 8.2. Setting

In total, this non-interventional study follows the population of 240 patients with nonvalvular atrial fibrillation. From 240 NVAF patients, 120 patients are treated with warfarin and 120 patients are treated with apixaban.

The study will follow the period of 6 months after the prescription of warfarin or apixaban for the secondary stroke/TIA prevention.

The data will be collected retrospectively from clinical practice hospital records.

It's expected that the data will be collected within 3 months from the start of the study – the data collection will be closed as soon as there are 120 patients enrolled in each study arm. If there are not 120 patients enrolled in each study arm after 3 months of the data collection, the period can be prolonged up to 6 months from the start of the study.

Requirements for the center's eligibility are as followed: center able to genetically determine patients' higher sensitivity to warfarin; neurologists, who work in cerebrovascular center in a hospital; satisfactory experience in the care of patients with NVAF and treatment with warfarin and NOAC; sufficient number of patients with NVAF diagnosis fulfilling eligibility criteria.

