### 8.3. Variables

**Table 1:** Table of variables

Variable	Role	Data source(s)	Operational definition
Age, Sex, BMI, date of index event (stroke/TIA diagnosis), date of indication to warfarin/apixaban treatment (index date)	Demographic data	Medical records	Specified in e-CRF
CHA2-DS2-Vasc score, HAS-BLED score	Outcome	Medical records	Specified in e-CRF
Therapy after index event, prior to warfarin/apixaban treatment	Exposure	Medical records	Specified in e-CRF
Warfarin/apixaban therapy information (dosage; number of INR measurements in warfarin arm)	Exposure	Medical records	Specified in e-CRF
Number and type of resource use during the first 6 months of warfarin/apixaban treatment (outpatient visits, diagnostic procedures, labs, medication, hospital admissions)	Outcome	Medical records	Specified in e-CRF
Amount, type, severity and cost of ischemic events	Outcome	Medical records	Specified in e-CRF

Amount, type, severity and cost of major/minor hemorrhagic events	Outcome	Medical records	Specified in e-CRF
Adverse events	Outcome	Medical records	Specified in e-CRF

*Index date = The index date will be the first date of OAC prescription indicated for secondary stroke/TIA prevention.*

*Index event = The index event will be the first stroke/TIA event based on which the OAC treatment will be initiated.*

*Index event date = The index event date will be the date of first stroke/TIA event based on which the OAC treatment will be initiated*

*Therapy after index event, prior to warfarin/apixaban treatment (Aspirin, clopidigrel, Trombolytics (rhu-tPA - alteplase, urokinase), Anticoagulants (heparin, heparinoids), other)*

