### **8.7. Data analysis**

The statistical analyses will be descriptive and exploratory. Given the nature of the study, which is exploratory, it is not designed to confirm or reject predetermined hypotheses.

Categorical outcomes will be summarized by the number and percentage in each category. Continuous outcomes will be summarized by mean, standard deviation, median, minimum and maximum values.

All analyses will be based on the full analysis set, comprising all subjects enrolled into the study.

The paired tests will be applied in the detailed analyses. Relevant endpoints will be compared using the differences in mean / median or proportion. Statistical significance will be assessed at a significance level of 0.05. All statistical analyses will be conducted using STATA version 13.1.

**Table 2:** Table of descriptive analyses

Variable	Categorical outcome	Continuous outcome
Age		X
Sex	X	
Body height, weight, BMI		X
Period between stroke/TIA and start of secondary stroke prevention (duration in days)		X
Period between stroke/TIA and start of secondary stroke prevention (medication)	X	
CHA2-DS2-VASc Score		X
Stratification: (0, 1, 2-9)	X	
HAS-BLED Score		X
Stratification: (0-2, 3-9)	X	
Warfarin/apixaban dosage		X
INR measurements	X	
Number and type of outpatient visits, diagnostic procedures, labs, hospital admissions	X	
Cost of outpatient visits, diagnostic procedures, labs, medication, hospital admissions		X
Amount, type and severity of ischemic events	X	
Cost of ischemic events		X
Amount, type, severity of major/minor hemorrhagic events	X	

Cost of major/minor hemorrhagic events		X
Adverse events	X	

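### Minor bleeds are counted from routine records while warfarin patients have more contacts, so an unadjusted comparison can favour apixaban on minor bleeds with no drug effect; for adverse events the direction is unknown.

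*Combined protocol and SAP*

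**What the plan says.** Section 7 of the combined protocol and SAP has two secondary objectives that bear on this point: "Number of major/minor hemorrhagic events in the first 6 months of the treatment" and "Overall safety (adverse events) of the treatment". Table 2 in 8.7 carries the first forward as "Amount, type, severity of major/minor hemorrhagic events".

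On the source, section 8.2 states: "The data will be collected retrospectively from clinical practice hospital records". Sections 8.1 and 8.4 add that the study imposes no assessments of its own. Table 1 leaves the definition of bleeding events to the e-CRF.

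On contact with care, section 6 describes frequent INR checks as a burden of warfarin and expects that "there are less outpatient visits, less monitoring needed and lower risk of the complications and adverse events expected with apixaban". Table 1 takes from the medical records the "number of INR measurements in warfarin arm".

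On analysis, 8.7 calls the work descriptive and exploratory, but also says that relevant endpoints will be compared by differences in mean, median or proportion and judged at 0.05. Section 8.9 names the distribution of patients between treatments as the main limitation and does not mention unequal recording of events.

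**The concern.** A minor bleed enters a routine chart only if the patient has a contact and the bleed is mentioned and noted there. No common assessment schedule evens out that chance. If warfarin patients have more contacts, more of their minor bleeds are recorded, and the arms can differ on paper when the drugs do not differ. More patients only make the wrong answer more precise, and adjustment for baseline covariates does not address it, because the fault lies in how the outcome is observed.

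At stake is the minor-bleed part of the hemorrhagic-event objective. The extra visits are a real cost of warfarin and belong in the cost analysis. The extra recorded minor bleeds are not necessarily a real effect of the drug.

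**Working it through.** **Figure in the plan.** There is none to reproduce. Section 8.5 gives 120 per arm on feasibility grounds, with no event rate, effect size or power.

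**Do the documents support each link?**
- Unequal contact: yes. Section 6 expects it.
- Contacts visible in these charts: largely. The documents do not say where INR checks take place, but Table 1 draws the INR counts from the medical records that also supply the bleeds.
- Recording by routine care only: yes (8.1, 8.2, 8.4).
- Comparison without a safeguard: yes. Section 8.7 has no adjustment for contacts, no adjudication and no item on how an event came to notice.

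**How large could it be?** This is an illustration with assumed inputs. Let *p* be the true 6-month proportion with a minor bleed, equal in both arms, and let *d*W and *d*A be the proportions of those patients whose bleed is recorded on warfarin and apixaban. The recorded proportions are *p·d*W and *p·d*A, and their ratio is *d*W/*d*A.

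From the plan: *n* = 120 per arm and a level of 0.05. I take the test as two-sided and for independent groups. Section 8.7 mentions paired tests but describes no pairing.

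Worked case, *p* = 0.25, *d*W = 0.80, *d*A = 0.50:
- Recorded proportions: 0.25 × 0.80 = 0.200 and 0.25 × 0.50 = 0.125, that is 24 and 15 of 120.
- Difference 0.075; mean proportion 0.1625.
- Standard error under no difference: √(2 × 0.1625 × 0.8375 / 120) = 0.0476.
- Standard error at the recorded proportions: √((0.200 × 0.800 + 0.125 × 0.875) / 120) = 0.0474.
- Chance of significance: 1 − Φ((1.96 × 0.0476 − 0.075) / 0.0474) = 1 − Φ(0.387) = 0.349. Using 0.0474 throughout gives 0.353.

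Other recording rates at *p* = 0.25, by the same formula:

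| Recorded, warfarin / apixaban | Patients recorded | Recorded risk ratio | Falsely significant |
|---|---|---|---|
| 60% / 60% | 18 vs 18 | 1.00 | 5.0% |
| 70% / 60% | 21 vs 18 | 1.17 | 8.2% |
| 80% / 50% | 24 vs 15 | 1.60 | 34.9% |
| 80% / 40% | 24 vs 12 | 2.00 | 58.4% |

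With *p* from 15% to 35%, the three unequal cases span 6.8% to 76.2%. With *p* = 10% they span about 6% to 26%. A simulation of 4,000 studies at *p* = 20% and 80% versus 40% gave 47.9% significant in favour of apixaban with the pooled z test and 40.3% with Fisher's exact test.

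**Adverse events.** Section 10 makes e-CRF recording mandatory when a provider explicitly attributes the event to a drug of the sponsor. Table 1 lists adverse events for both arms without saying whether that rule limits them. If the warfarin used is not the sponsor's product, which the documents do not say, the recording duty is heavier for apixaban. Assumed reverse case: recording of 20% on warfarin and 40% on apixaban, with a true risk of 20% to 30%, gives 25.5% to 36.8% falsely significant in favour of warfarin.

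**The case against.** The strongest reply is that no between-arm test of minor bleeds is clearly planned. In section 7 only direct costs carry the word comparison, Table 2 is a table of descriptive analyses, and 8.7 disclaims hypothesis testing. This lowers the stakes but does not close the point. Section 6 gives the purpose as comparing resource use between the drugs and counts clinical events within it, 8.9 presents the comparison of outcomes between the cohorts as a strength, and 8.7 applies the 0.05 level to relevant endpoints that it never lists.

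Second, INR checks may take place outside the hospital, so that the extra contacts add little to its charts. Table 1 largely answers this, since the INR counts are to come from the medical records. If some checks are missing from them, the bias shrinks.

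Third, the magnitude rests wholly on assumed rates, and the model uses proportions of patients whereas section 7 asks for numbers of events. This stands. The figures show what could happen, not what will.

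Fourth, costs are barely touched. A minor bleed that is only mentioned at an INR visit adds little cost, and one that triggers care is a real cost. This also stands, so a material bias in the cost objectives should not be inferred.

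**Conclusion.** The concern holds for minor bleeds. The protocol's own expectation of fewer contacts on apixaban, recording from charts only, and an unadjusted comparison at 0.05 together allow an apparent advantage for apixaban that is not a drug effect. The size is unknown. The illustration of 24 versus 15 patients and about 35% false significance rests on an assumed 25% true risk and assumed recording of 80% versus 50%; with 70% versus 60% the rate is 8.2%, not far above the nominal 5%.

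Three stronger readings are not supported:
- A reader might infer that adverse events too are biased in the sponsor's favour. Their recording may differ by arm, but the attribution rule in section 10 could push the other way, so the direction is open.
- A reader might infer that the study itself builds in the unequal visits. It imposes none; the difference comes from routine care.
- A reader might infer that apixaban is bound to look safer overall. The documents support only a plausible direction for minor bleeds. Major bleeds, admissions and deaths should be much less exposed.

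**What to change.** 1. In 8.7, limit the between-arm bleeding comparison and test to bleeds that led to hospital admission, transfusion or a procedure, with routine INR checks not counted as a procedure. Table 1 already collects admissions and other resource use, and section 7 covers treatment-related medical procedures; confirm that the e-CRF identifies transfusions.
2. Do not let an unscheduled visit qualify a bleed. A warfarin patient can wait and mention a bleed at the next INR visit, while an apixaban patient with the same bleed may need an extra visit, so this criterion could reverse the bias. For example, with an assumed 25% true risk and own-visit shares of 30% on warfarin and 50% on apixaban, the recorded proportions are 7.5% and 12.5%, and about 25% of studies would be falsely significant against apixaban.
3. Report minor bleeds and other adverse events by arm as description only, without a between-arm test, next to the number of contacts per arm.
4. State one adverse-event recording rule that applies to both arms for the analysis. The safety-reporting duty in section 10 can stay as it is.
5. Name unequal ascertainment as a limitation in 8.9.

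The cost is a few sentences in 8.7 and 8.9 and one clarification of the e-CRF instructions. The downside is that fewer events enter the bleeding comparison, so it is less precise.

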## 8. RESEARCH METHODS

### 8.1. Study design

This is a double arm, non-interventional, single-center retrospective study according to Czech legal definitions (Law 378/2007 Sb.). For the description of the direct costs related to warfarin/apixaban treatment, retrospective data will be used for both, the warfarin treatment arm and the apixaban treatment arm.

The study follows two cohorts of NVAF patients, who used either warfarin or apixaban as a secondary stroke/TIA prevention.

The data to be collected retrospectively:

- Consecutive data of the 6 months after the first prescription of warfarin/apixaban (indicated as a secondary stroke/TIA prevention).

Considering the retrospective design of data collection, the non-interventional study will not impose any additional procedures, assessments or changes to the routine management of subjects. Data for the study will be obtained from clinical practice records and transcribed to an anonymous electronic case report form (e-CRF).

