### 8.2.1. Inclusion criteria

The data will be collected for patients who have met all of the following inclusion criteria:

1. Diagnosis of non-valvular atrial fibrillation (NVAF);
2. New initiation of anticoagulation therapy (apixaban or warfarin) due to the ischemic event (stroke/TIA) meaning patients previously not anticoagulated due to diagnosis of NVAF;
3. Indication to anticoagulation therapy as a secondary stroke prevention within 7 to 30 days after the stroke/TIA event;
4. Apixaban arm: genetically determined higher sensitivity to warfarin;
5. Patients whose status allowed oral treatment with apixaban/warfarin;
6. Age  $\geq 18$ ;
7. Access to patient's records of the first 6 months of the warfarin/apixaban treatment.

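### Does the six-month costing window wrongly leave out the genetic test that admits patients to the apixaban arm, and does the hospital-day count need a rule for the index admission?

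*Combined protocol and SAP*

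**What the plan says.** Section 8.1 collects "Consecutive data of the 6 months after the first prescription of warfarin/apixaban". Section 8.2 repeats the six-month follow-up from prescription, and the footnote to Table 1 in section 8.3 defines the index date as the date of the first anticoagulant prescription.

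The primary objective in section 7 is "Description of direct costs related to warfarin/apixaban treatment during the first 6 months of the secondary stroke prevention in NVAF patients". Comparing those costs between the arms is a secondary objective. Two further secondary objectives matter here: "Number and costs of medical procedures directly related to the treatment in the first 6 months" and "Number of hospitalization days in the first 6 months of the treatment".

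On the genetic test, section 8.2.1 lists "Apixaban arm: genetically determined higher sensitivity to warfarin". Section 6 explains why: "Individuals with higher sensitivity to warfarin are eligible for first line NOACs treatment in secondary prevention of stroke". Section 8.2 asks for a "center able to genetically determine patients' higher sensitivity to warfarin". No section gives the test date, says whether warfarin patients were tested, or names the test as a cost item. Section 8.3 leaves operational definitions to the e-CRF, which is not among the documents.

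**The concern.** The genetic result is an entry condition for one arm only, and it is one of the situations that permit a first-line NOAC. It would ordinarily come before the prescription, and so before the window opens. On that reading a cost peculiar to the apixaban route is absent from the apixaban total, while INR tests, the corresponding item for warfarin, fall inside the window and are named in Table 1. Table 1 also records one item from before the prescription, the therapy given between the stroke or TIA and the start of anticoagulation, so the plan does look behind the window when it chooses to.

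Costs by arm are the primary objective. If the test belonged in the total, leaving it out would favour apixaban whenever fewer warfarin than apixaban patients had been tested.

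A smaller worry concerns hospital days. Anticoagulation is indicated 7 to 30 days after the event, so the index stay may still be running on the index date. The hospital-day objective does not say whether those remaining days count.

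**Working it through.** **Step 1: what the window does with the test.** Section 7 limits costs to the first six months of treatment, sections 8.1 and 8.2 limit data to the six months after prescription, and Table 1 limits resource use to the same six months. Together they give a rule: a test before the prescription is out, and a test after it is a lab. One loose end is that the Table 1 row describes the index date as the date of indication, while its footnote uses the first prescription. Section 8.1 agrees with the footnote.

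**Step 2: the comparison with Table 1.** INR counts are monitoring during treatment. Therapy between event and prescription is recorded as an exposure, and Table 2 in section 8.7 summarises that interval by duration and medication, with no cost. Neither entry shows that the plan costs care given before the prescription.

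**Step 3: how far counting the test would move the result.** There is no figure in the plan to reproduce: section 8.5 says the sample size was not statistically determined, and no unit cost or standard deviation (SD) is given. Let c be the test price and q the share of warfarin patients tested, and assume each apixaban patient had one test before the prescription. Then

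difference with test = difference without test + c × 1 − c × q = difference without test + c(1 − q).

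The shift is c if no warfarin patient was tested and 0 if all were.

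**Step 4: whether the documents fix q.** Section 6 reports that "about 30% of the Czech healthy subjects have genetically determined higher sensitivity to warfarin". Assuming this share holds for candidate patients:

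- at 30%: 120 / 0.30 = 400 tests to find 120 sensitive patients, leaving 400 − 120 = 280 negatives;
- at an assumed 25%: 480 tests, 360 negatives;
- at an assumed 35%: 343 tests, 223 negatives.

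In each case the negatives exceed the 120 places in the warfarin arm, so that arm could consist wholly of tested patients. Nothing prevents it from consisting wholly of untested ones. Any q from 0 to 1 is possible.

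**Step 5: scale.** With 120 per arm and equal SDs, the 95% confidence interval for a difference in mean cost has half-width 1.96 × √(2/120) = 0.25 SD. The test matters to the comparison only if c(1 − q) is a noticeable fraction of that. Suppose that costs including the test were truly equal, q = 0, and c = 0.10 SD (an assumed value). Leaving the test out would then give a significant difference with probability 12% instead of 5%; at c = 0.20 SD it would be 34%. Both figures presuppose that the test belongs in the target.

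**Step 6: hospital days.** Leftover days = max(0, length of stay − day of prescription). An assumed 14-day stay leaves 7 days if the prescription is on day 7 and none if it is on day 14 or later. Read literally, the endpoint counts such days, and it does so in both arms. The same applies to cost, since Tables 1 and 2 list hospital admissions and their cost without requiring a direct link to treatment. No document gives stay lengths or prescription days by arm, so no direction of bias can be derived.

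**The case for a change.** The best case for acting is that section 6 presents the study as evidence on how treatment strategies affect resource use and cost. Here the first-line apixaban strategy includes a test. Section 7 speaks of costs related to treatment, and labs are costed, so a person abstracting charts might include the test for some patients and not for others. The records should normally hold the dates, so a separate line would be cheap. Calling the study exploratory does not remove the point, since describing costs by arm is its main purpose and section 8.7 tests at 0.05.

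Part of this stands. The plan does not acknowledge the boundary, and a reader cannot tell how many warfarin patients were tested. Three things weaken the rest. The date limit appears in every section that defines the data, so including an earlier test would depart from the plan. The e-CRF may already settle the matter. And a test line would not deliver the strategy cost: at 30% prevalence the full screening cost is 400/120 = 3.3 tests per apixaban patient, partly incurred in people who may never be enrolled, while other care before the prescription stays uncosted. The result would be a hybrid total.

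**Conclusion.** The wording is incomplete, but following it does not give a wrong answer to the question asked. For direct costs in the first six months of treatment, a test done earlier is correctly outside the total. Wanting it inside is a preference for a broader costing perspective. The difference between the two perspectives is c(1 − q) per patient, from zero to one test price, assuming one test before the prescription for each apixaban patient. That the test came first is itself an inference from sections 6 and 8.2.1.

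For hospital days, the literal reading is usable and symmetric between the arms, and no bias has been shown. Analysts can fill both gaps by applying the stated window to both arms and saying in the report that testing before the prescription lies outside the totals. The conclusion would need another look if the e-CRF turned out to treat the test or the index stay differently in the two arms.
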